10.4.3 Neutralizing antibody assay

Depending upon the concentrations measured in collected specimens, the functional capacity of infused VRC01/VRC01LS (in serum and mucosal secretions) to neutralize HIV may be evaluated by an *in vitro* cell-based virus neutralization assay (65-67) using pseudotyped viruses.

One or more viruses, including those matching the Envs encoded by *ex vivo* challenge viruses that range from highly to moderately sensitive to VRC01 (eg, MN.3, BaL26 and DU151.2), will be assayed. The IC₅₀ of VRC01 against MN.3, BaL26 and DU151.2 are in the range of 0.04 mcg/mL (MN.3 and BaL26) and ~4.0 mcg/mL (DU151.2). The IC₈₀ values of VRC01 against these viruses are around 0.07, 0.15 and 45.3 mcg/mL, respectively. The TZM-bl assay is validated for this range of sensitivities. It has been shown that the neutralization potency and breadth are similar between VRC01 and VRC01LS (49).

10.5 Genotyping

Fc-receptor, CCR5 delta-32 and human leukocyte antigen (HLA) molecular genotyping may be performed on enrolled participants using cryopreserved PBMC collected at baseline. Other markers, such as genes associated with immune functions or HIV-1 disease progression, may also be assessed.

10.6 Exploratory studies

Samples may be used for other testing and research related to furthering the understanding of HIV, immunology, vaccines, antibody mediated prevention, and clinical trial conduct. In addition, cryopreserved samples may be used to perform additional assays to support standardization and validation of existing or newly developed methods.

10.7 Other use of stored specimens

The HVTN stores specimens from all study participants indefinitely, unless a participant requests that specimens be destroyed or if required by IRB/EC, or RE.

Other use of specimens is defined as studies not described in the protocol.

This research may relate to HIV, vaccines, the immune system, and other diseases. This could include limited genetic testing and, potentially, genome-wide studies. This research is done only to the extent authorized in each study site's informed consent form, or as otherwise authorized under applicable law. Other testing on specimens will occur only after review and approval by the HVTN, the IRB/EC of the researcher requesting the specimens, and the CRS's IRBs/ECs if required.

The protocol sample informed consent form is written so that the participant either explicitly allows or does not allow their samples to be used in other research when they sign the form. Participants who initially agree to other use of their samples may rescind their approval once they enter the study; such participants will remain in this study and their samples will only be used for the studies described in this protocol. If a participant decides against allowing other research using his or her samples, or at any time rescinds prior approval for such other use, the study site investigator or designee must notify HVTN Regulatory Affairs in writing. In either case, HVTN Regulatory Affairs directs the HVTN Lab Program not to use samples from these participants for such other uses.

CRSs must notify HVTN Regulatory Affairs if institutional or local governmental requirements pose a conflict with or impose restrictions on other use of specimens.

10.8 Biohazard containment

As the transmission of HIV and other blood-borne pathogens can occur through contact with contaminated needles, blood, and blood products, appropriate precautions will be employed by all personnel in the drawing of blood, collecting of tissue, and shipping and handling of all specimens for this study, as currently recommended by the CDC and the NIH or other applicable agencies.

All dangerous goods materials, including Biological Substances, Category A or Category B, must be transported according to instructions detailed in the International Air Transport Association Dangerous Goods Regulations.

11 Safety monitoring and safety review

11.1 Safety monitoring and oversight

11.1.1 HVTN 116 PSRT

The HVTN 116 PSRT is composed of the following members:

- DAIDS medical officer representative,
- Protocol chair and cochair,
- Protocol Team leader,
- Core medical monitor,
- Clinical safety specialist, and
- Regional Medical Liaison (RML).

The clinician members of HVTN 116 PSRT are responsible for decisions related to participant safety.

The Protocol Team clinic coordinator, project manager, product developer representative, clinical trial manager, and others may also be included in HVTN 116 PSRT meetings.

11.1.2 HVTN SMB

The SMB is a multidisciplinary group consisting of biostatisticians, clinicians, and experts in HIV prevention research that, collectively, has experience in the conduct and monitoring of HIV prevention trials. Members of the SMB are not directly affiliated with the protocols under review.

The SMB reviews safety data, unblinded as to treatment arm, approximately every 4 months. The reviews consist of evaluation of cumulative reactogenicity events, AE, laboratory safety data, and individual reports of adverse events requiring expedited reporting to DAIDS. To increase the sensitivity for detecting potential safety problems, the SMB will review safety data aggregated across multiple protocols that use the same or similar prevention approaches. The SMB conducts additional special reviews at the request of the HVTN 116 PSRT.

Study sites will receive SMB summary minutes and are responsible for forwarding them to their IRB/EC and any applicable RE.

11.1.3 SDMC roles and responsibilities in safety monitoring

The roles and responsibilities of the SDMC in relation to safety monitoring include:

- Maintaining a central database management system for HVTN clinical data;
- Providing reports of clinical data to appropriate groups such as the HVTN 116 PSRT and HVTN SMB (Section [11.1.2](#));

11.1.4 HVTN Core roles and responsibilities in safety monitoring

The roles and responsibilities of HVTN Core in relation to safety monitoring include:

- Daily monitoring of clinical data for events that meet the safety pause and HVTN 116 PSRT AE review criteria (Section [11.3](#));
- Notifying HVTN CRSs and other groups when safety pauses are instituted and lifted (Section [11.3](#));
- Querying HVTN CRSs for additional information regarding reported clinical data; and
- Providing support to the HVTN 116 PSRT.

11.2 Safety reporting

11.2.1 Submission of safety forms to SDMC

Sites must submit all safety forms (eg, reactogenicity, adverse experience, urinalysis, local lab results, and concomitant medications) before the end of the next business day after receiving the information. The forms should not be held in anticipation of additional information at a later date. If additional information is received at a later date, the forms should be updated and resubmitted before the end of the next business day after receiving the new information.

11.2.2 AE reporting

An AE is any untoward medical occurrence in a clinical investigation participant administered a study product/procedure(s) and which does not necessarily have a causal relationship with this treatment. An AE can therefore be any unfavorable and unintended sign (including an abnormal laboratory finding), symptom, or disease temporally associated with the use of an investigational study product/procedure(s), whether or not related to the investigational study product/procedure(s). All AEs are graded according to the Division of AIDS Table for Grading the Severity of Adult and Pediatric Adverse Events, Corrected

Version 2.1, July 2017, available on the RSC website at <http://rsc.tech-res.com/clinical-research-sites/safety-reporting/daids-grading-tables>, except:

- Unintentional weight loss is required to be reported as an AE only if it is considered to be potentially deleterious to the participant's health (see HVTN 116 Study Specific Procedures);
- Infusion Site Erythema or Redness and Infusion Site Induration or Swelling will not consider interference with usual social and functional activities such that:
 - Grade 1 is: 2.5 to < 5 cm in diameter OR 6.25 to < 25 cm² surface area;
 - Grade 2 is: ≥ 5 to < 10 cm in diameter OR ≥ 25 to < 100 cm² surface area;
 - Grade 3 is: ≥ 10 cm in diameter OR ≥ 100 cm² surface area OR Ulceration OR Secondary infection OR Phlebitis OR Sterile abscess OR Drainage;
 - Grade 4 is: Potentially life-threatening consequences (eg, abscess, exfoliative dermatitis, necrosis involving dermis or deeper tissue);
- Infusion reactions

All AEs are reported to the SDMC on the appropriate CRF. Clinic staff should evaluate every AE to determine if (1) the AE meets the requirements for expedited reporting to DAIDS (Section 11.2.3) and (2) if the AE meets the criteria for a safety pause/prompt AE review (Section 11.3).

Sites are expected to notify the CSS or RML of any serious safety concern requiring their attention (Table 11-1). Telephone numbers and email addresses are found on the protocol home page on the HVTN Members' site (<https://members.hvtn.org/protocols/hvtn116>). Concerns requiring immediate attention should be communicated by calling the clinical safety phone.

In the case of email notification, the CSS or RML will reply during working hours (ie, US Pacific Time, South African Standard Time) to confirm that the email has been received and reviewed. If email service is not available, the HVTN CRS should notify the CSS or RML of the event by telephone, then submit CRFs.

In addition, site investigators are required to submit AE information in accordance with IRB/EC and any applicable RE requirements.

11.2.3 Expedited reporting of adverse events to DAIDS

Requirements, definitions and methods for expedited reporting of AEs are outlined in Version 2.0 (January 2010) of the *Manual for Expedited Reporting of Adverse Events to DAIDS* (DAIDS EAE Manual), which is available on the RSC website at <http://rsc.tech-res.com/clinical-research-sites/safety-reporting/manual>. The SAE Reporting Category will be used for this study.

The DAIDS Adverse Experience Reporting System (DAERS), an internet-based reporting system, must be used for expedited AE reporting to DAIDS. In the event of system outages or technical difficulties, expedited AE reports may be submitted via the DAIDS EAE Form. This form is available on the DAIDS RSC website at <http://rsc.tech-res.com/clinical-research-sites/safety-reporting/daids/paper-eae-reporting>. For questions about DAERS, please contact NIAID CRMS Support at [contact]. Please note that site queries may also be sent from within the DAERS application itself.

For questions about expedited AE reporting, please contact the DAIDS RSC Safety Office at ([contact]).

The study products for which expedited reporting is required are:

- VRC01 (VRC-HIVMAB060-00-AB)
- VRC01LS (VRC_HIVMAB080-00-AB)

While the participant is in the study reporting period (from the first study product administration until the last scheduled clinic visit), the SAE Reporting Category will be used.

After the protocol-defined AE reporting period for the study, unless otherwise noted, only Suspected, Unexpected Serious Adverse Reactions as defined in Version 2.0 of the DAIDS EAE Manual must be reported to DAIDS, if the study staff become aware of the events.

The NIAID/DAIDS will report all unexpected SAEs related to the study products observed in this clinical trial to the FDA in accordance with 21 CFR 312.32 (IND Safety Reports).

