9.3 Enrollment visits

Enrollment in Groups 1, 2, and 3 is simultaneous with baseline biopsy collections on day -14. Enrollment in Groups 4 and 5 is simultaneous with the infusion on day 0. The time interval between randomization and first infusion should not exceed 4 working days. The CRS requests the randomization assignment from the Web-based randomization system. Randomization will be performed prior to first infusion for all groups.

At the baseline biopsy collection visit (Groups 1-3; day -14), cervical, vaginal, and/or rectal biopsies will be collected. These samples will serve as baseline controls and will help to assess the acceptability of the biopsy procedures to participants and the fitness of participants to continue in these groups with extensive mucosal biopsy collections. Participants with conditions not amenable to repeated biopsy sampling or participants not willing to continue in the trial after these baseline biopsies have been performed may be replaced.

At the baseline biopsy collection visit (Groups 1-3; day -14), the following procedures are performed:

- Abbreviated physical examination, including weight, vital signs, and a symptom-directed evaluation by history and/or appropriate physical exam based on participant self-reported symptoms or complaints
- Assessment of concomitant medications (Section 9.2)
- Assessment of any new or unresolved AEs/intercurrent illnesses
- Urine or serum pregnancy test (for participants who were born female). Persons who are NOT of reproductive potential due to having undergone bilateral oophorectomy (verified by medical records), are not required to undergo pregnancy testing
- Risk reduction counseling (Section 9.7)
- Pregnancy prevention assessment (Section 9.2 and 9.8)

- Assessment of new or unresolved social impacts (site staff will ask participant about the status of any unresolved social impacts and if s/he has experienced any new social impacts as a result of the trial participation)
- Specimen collection (including mucosal sampling as described in Section 9.6);
- HSV 1/2 testing
- Blood hormone levels (estradiol and progesterone) (persons born female only)
- Confirm that participants received HIV test results from previous visit. If not, provide test results and post-test counseling as appropriate.

For the enrollment infusion visit (Groups 4 and 5; day 0) procedures are described in Section 9.4.

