## 8. STATISTICAL ANALYSIS

This section describes the final study analysis. Of note, Groups 1-3 participants are enrolled 1 month before the first infusion. Groups 4 and 5 participants are enrolled at the first infusion. All analyses pertaining to the safety and drug level objectives of this study are intent-to-treat analyses that include all randomized individuals per their randomization allocation. In addition, analyses will also be performed as treated accounting for the actual infusions and dose levels each participant received.

No formal multiple comparison adjustments will be employed for multiple safety endpoints.

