#### 8.4.2. AEs and SAEs

AEs will be summarized using MedDRA System Organ Class and preferred terms. Tables will show by treatment arm the number and percentage of participants experiencing an AE within a System Organ Class or within preferred term category by severity or by relationship to study product or mucosal sampling. For the calculations in these tables, a participant with multiple AEs within a category will be counted once under the maximum severity or the strongest recorded causal relationship to study product or mucosal sampling. Formal statistical testing comparing arms is not planned since interpretation of differences must rely heavily upon clinical judgment.

A listing of SAEs reported to the DAIDS Regulatory Support Center (RSC) Safety Office will provide details of the events including severity, relationship to study product or mucosal sampling, time between onset and last infusion, and number of infusions received.

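### In Groups 1-3 the expedited SAE reporting period opens at first infusion, so a serious event between the day -14 baseline biopsies and day 0 has no stated reporting rule and drops out of the SAP's only SAE listing

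*Protocol*

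**What the plan says.** **Reporting period.** Protocol 11.2.3 sets the period for the SAE Reporting Category as "from the first study product administration until the last scheduled clinic visit". The sentence that begins "The study products for which expedited reporting is required are" is followed by VRC01 and VRC01LS only. A rule is given for later events ("After the protocol-defined AE reporting period for the study, unless otherwise noted, only Suspected, Unexpected Serious Adverse Reactions" need be reported). None is given for the time before the first product.

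**Timing in Groups 1-3.** Protocol 9.3 says "Enrollment in Groups 1, 2, and 3 is simultaneous with baseline biopsy collections on day -14", and also "Randomization will be performed prior to first infusion for all groups". It allows at most 4 working days between randomization and infusion. Protocol 6.4 and SAP 8 give a different interval: "Groups 1-3 participants are enrolled 1 month before the first infusion".

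**AE definition.** Protocol 11.2.2 covers procedures as well as products ("An AE is any untoward medical occurrence in a clinical investigation participant administered a study product/procedure(s") and sends all AEs to the data center on case report forms.

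**SAE listing.** SAP 8.4.2 lists the SAEs reported to the DAIDS Regulatory Support Center safety office. The fields include "relationship to study product or mucosal sampling, time between onset and last infusion, and number of infusions received". The matching listing in Protocol 6.4.3.2 has no mucosal-sampling field; the SAP added it. SAP 9.1 names one corresponding output, the expedited events reported to that office, and no other SAE listing.

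**The concern.** The SAP widened its SAE listing so that biopsy-related events could be seen as such. The listing's source is a reporting stream that, for Groups 1-3, opens only after the first biopsy visit is over. A serious bleed or infection from that visit with onset before day 0 would meet the AE definition and the purpose of the listing, yet nothing in the stated period would bring it into the listing.

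The same event would not be among the individual expedited reports that the Safety Monitoring Board receives under Protocol 11.1.2. The people least visible are those who leave after the baseline biopsies and before randomization. A complication is a plausible reason for leaving at that point.

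**Working it through.** The plan states no figure on this point, so the check is mainly one of text, with counts to give the scale.

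**1. Where a pre-infusion SAE goes.** Take a serious event with onset after the day -14 biopsies and before day 0.
- *AE form:* captured. AEs are assessed at the baseline biopsy visit (9.3) and before infusion (9.4), and Appendices L and M mark this at Visits 02 and 03.
- *Stated expedited period (11.2.3):* outside it.
- *SAP AE tables (9.1):* it can appear by severity and by relationship to mucosal sampling, given an arm. Neither layout identifies seriousness, and a severe grade is not the same as a serious event.
- *SAP SAE listing (8.4.2, 9.1):* absent unless a site reports it without being asked to. The time field counts from the last infusion, which does not yet exist for this event.

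An event that follows the baseline biopsy but has its onset on or after day 0 falls inside the period.

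**2. Who may have no arm.** Randomization comes at most 4 working days before infusion, so after the day -14 biopsies. Protocol 7.3.6 makes declining further biopsies in this interval a reason for termination, and 9.3 allows replacement. If not yet randomized, such a participant is outside the all-randomized analysis set (Protocol 6.4, SAP 8), has no column in by-arm tables, and never enters the reporting period.

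**3. How many participants.** Protocol Table 3-1: 23 + 23 + about 6 = about 52 of 74 (70%). SAP schema: 23 + 23 + 7 = 53 of 79 (67%).

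**4. Share of biopsies taken at baseline (Protocol Table 9-1).**

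| Site | Groups 1-2 | Group 3 |
|---|---|---|
| Rectal | 5/25 = 20% | 5/35 = 14% |
| Ectocervical | 4/14 = 29% | 4/16 = 25% |
| Vaginal | 5/22 = 23% | 5/24 = 21% |

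Baseline is 1 of 5 biopsy visits in Groups 1-2 and 1 of 7 in Group 3, where the seventh is conditional for cervical and vaginal samples. Protocol 4.8 expects healing in 5-14 days, so a 14-day interval spans the whole expected healing time.

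**5. Chance of at least one such SAE.** The documents give no biopsy SAE rate, so p below is an assumed rate per participant for the interval. With n = 52, the chance is 1 - (1 - p)^52:

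| Assumed p | Chance of one or more |
|---|---|
| 0.1% | 5% |
| 0.5% | 23% |
| 1% | 41% |
| 2% | 65% |
| 4% | 88% |

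The low end is the more credible. Protocol 4.8 reports no complication in more than 150 biopsy visits at one site and in more than 160 cervicovaginal visits in another program. Treating these as 310 independent visits, the one-sided 95% upper bound on the complication rate per visit is 1 - 0.05^(1/310) = 0.96%. Repeat visits by the same people make that bound approximate. The 4% row matches the SAE rate in placebo recipients that Protocol 6.1.1 quotes for vaccine trials; it is not a rate for two weeks after a biopsy.

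**The case against.** The best defense is that two separate streams are at work. Section 11.2.2 governs all AEs and has no start date tied to infusion. Section 11.2.3 governs expedited reports about two named products, so opening it at first product is coherent. The SAP promises a listing of what was reported to the safety office, not of every SAE from enrollment. Its mucosal-sampling field still has content, since 4 of 5 biopsy visits in Groups 1-2, 6 of 7 in Group 3 and all in Groups 4-5 fall inside the period. Sites must also notify safety staff of any serious concern, forms are due by the next business day, and routine review begins with enrollment (11.2.1, 11.2.2, 11.4).

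Most of this stands, and it rules out three stronger readings that a reader might infer:
- *That these events go uncaptured, so biopsy risk is understated.* AE forms and the planned mucosal-sampling tables cover them for participants with an arm.
- *That the AE definition and the reporting period contradict each other.* They serve different streams.
- *That exploratory objective 6 is compromised.* It concerns acceptability and tolerability, does not rest on this listing, and has a questionnaire at Visit 03, after the baseline biopsies.

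The defense does not supply a rule for the pre-infusion interval, a place where such an event is shown as serious, or a home for participants who leave before randomization.

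**Conclusion.** The gap is real and narrow. For about 52 participants, the interval from baseline biopsy to first infusion has no stated expedited-reporting rule. An SAE with onset there would be missing from the SAP's only SAE listing and not identifiable as serious elsewhere in the planned tables. It would still be recorded as an AE.

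On assumed rates of 0.1% to 1%, the chance that the trial meets even one such event is about 5% to 41%. The expected effect on the safety report is therefore at most a line or two. The point merits a short text change because the change is cheap, not because the safety conclusions are in doubt.

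This rests on the protocol text alone. Section 11.2.3 refers to a DAIDS manual for requirements and definitions, and whether that manual covers procedure-related events before first dose cannot be checked here. The length of the interval is also unsettled: 14 days by 9.3 and the appendices, 1 month by Protocol 6.4 and SAP 8.

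**What to change.** - **Protocol 11.2.3:** start the SAE reporting period at enrollment, which 9.3 places on day -14 for Groups 1-3 and at the day 0 infusion visit for Groups 4-5. Do not define the start as the first study procedure: Groups 4-5 give mucosal secretions during screening (Appendices J and K), and that wording would pull their screening into the period.
- **SAP 8.4.2 and 9.1:** list all SAEs from enrollment, whether or not reported to the safety office. Add a flag for onset before the first infusion and a field for time since the last biopsy.
- **SAP 8.4.2:** show participants who were enrolled but never infused in a separate block, so that those without an arm are not dropped.
- **Protocol 6.4, 9.3 and SAP 8:** reconcile day -14 with the 1-month statement.

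The cost is a few lines of text in each document and, at most, a few extra expedited reports. Sample size, analysis methods and the visit schedule are untouched.

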⁴ Local labs may assign appropriate alternative tube types for locally performed tests.

⁵ Chemistry panels are defined in Section 9.2 (pre-enrollment).

⁶ Genotyping may be performed on enrolled participants using cryopreserved PBMC collected at baseline.

⁷ Pregnancy test may be performed on blood specimens. Persons who are NOT of reproductive potential due to having undergone bilateral oophorectomy (verified by medical records), are not required to undergo pregnancy testing.

⁸ At an early termination visit for a withdrawn or terminated participant who is not HIV-infected (see Section 9.12), blood should be drawn for HIV diagnostic testing, as shown for visit 17 above. If a participant has a confirmed diagnosis of HIV infection, do not collect blood for HIV diagnostic testing (see Section 9.14).

⁹ Functional humoral assays may include nAb, ADCC, virion capture, and phagocytosis assays.

¹⁰ Syphilis testing will be done by serology.

¹¹ Chlamydia/Gonorrhea testing will be done with both rectal swabs and urine in males, and with urine and/or vaginal swabs in females; testing will occur at indicated visits and when clinically indicated.

¹² Cervical/vaginal swabs will be collected from females for bacterial vaginosis and *Trichomonas vaginalis* at the indicated visits and when clinically indicated.

¹³ Cervical/vaginal swabs will be collected from females for yeast only when clinically indicated.

¹⁴ Mucosal specimens will be collected once the participant has been found to have met mucosal specimen collection criteria specified in the SSP.

¹⁵ Mucosal biopsy collections must be at least 28 days from the previous biopsy collection.

¹⁶ The total 56-day blood collection includes 10mL maximum blood loss per biopsy collection visit.

¹⁷ And microscopy if needed.

¹⁸ Hormone panel (persons born female only) is defined in Sections 9.3 (enrollment visits) and 9.5 (follow-up visits).

¹⁹ The visit total indicates the total number of colorectal, cervical, or vaginal biopsies collected per visit.

²⁰ These biopsies will only be collected if the participant has missed prior collection visit(s), in order to maintain the overall number of biopsies in the "Total Biopsies" column.

²¹ For participants with confirmed diagnosis of HIV infection, only specimens required for protocol-specified safety laboratory tests, urinalysis and pregnancy tests will be collected.

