Social impact assessment questionnaire	—	—	—	—	—	X	—	—	—	—	—	—	X	—	—	—	X	—	—	—	
Acceptability questionnaire	—	—	X	—	—	—	—	—	—	—	—	—	—	—	X	—	X	—	—	—	
Concomitant medications	X	X	X	X	X	X	X	—	X	—	X	X	X	X	X	X	X	—	—	—	
Intercurrent illness/adverse experience	—	X	X	X	X	X	X	—	X	—	X	X	X	X	X	X	X	—	—	—	
HIV infection assessment ^f	—	—	—	—	—	—	—	—	—	—	—	—	—	X	—	X	X	—	—	—	
Confirm HIV test results provided to participant	—	X	—	—	—	—	—	—	—	—	—	—	—	—	X	—	X	—	—	X	
Mucosal biopsy collection^g																					
Colorectal	—	X	—	—	—	—	—	—	—	—	—	—	—	X	X	X	X	—	—	—	
Cervical	—	X	—	—	—	—	—	—	—	—	—	—	—	X	X	X	X	—	—	—	
Vaginal	—	X	—	—	—	—	—	—	—	—	—	—	—	X	X	X	X	—	—	—	
Mucosal secretion collection^h																					
Semen	—	X	—	X	X	—	X	—	X	—	—	X	—	X	X	X	X	—	—	—	
Cervical secretions	—	X	—	X	X	—	X	—	X	—	—	X	—	X	X	X	X	—	—	—	
Rectal secretions	—	X	—	X	X	—	X	—	X	—	—	X	—	X	X	X	X	—	—	—	

Grayed out visits are not applicable to this group

^a Screening may occur over the course of several contacts/visits up to and including visit 02, prior to biopsy collections.

^b Includes transmission risk reduction counseling for HIV-infected participants.

^c Pregnancy prevention assessment is required only for participants who were born female and are capable of becoming pregnant.

^d Not applicable to HIV-infected participants.

^e Participants will be randomized prior to the first infusion, ideally within 4 days. See Section 6.2.

^f Includes pre-test counseling. A subsequent follow-up contact is conducted to provide post-test counseling and to report results to participant. If a participant has a confirmed diagnosis of HIV infection, do not perform HIV infection assessment.

^g Mucosal specimens will be collected once the participant has been found to have met mucosal specimen collection criteria specified in the SSP. Mucosal biopsy collections must be at least 28 days from the previous biopsy collection.

Procedures at HVTN CRS for Group 1 and Group 2 continued

Visit:	01	02	03	04	05	06	07	08	09	10	11	12	13	14	15	16	17	18	19	Post	
Day:		D-14	D0	D1-15	D29-43	D56	D57-71	D84	D85-99	D99-113	D112	D127-141	D168	D169-183	D197-211	D253-267	D351-365	D442-456	D526-540		
Week:		W-2	W0	W1-2	W5-6	W8	W9-10	W12	W13-14	W15-16	W16	W19-20	W24	W25-26	W29-30	W37-38	W51-52	W64-65	W76-77		
Month:			M0			M2		M3			M4		M6								
Procedure	Scr.		Infl			Inf2					Inf3		Inf4								
Local lab assessments^a																					
Screening HIV test	X	—	—	—	—	—	—	—	—	—	—	—	—	—	—	—	—	—	—	—	

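### In Groups 1, 2, 4 and 5 the final biopsies are taken at the last clinic visit, so no scheduled adverse-event question follows them; the planned HIV-result contact could carry one

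*Protocol*

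**What the plan says.** **Biopsies.** Protocol Tables 9-1 and 9-2 (Section 9.6) put the final planned biopsies at Visit 17 in Groups 1, 2 and 5 and at Visit 14 in Group 4. By the follow-up durations in Section 3 (12 months, and 6 months for Group 4), these are the last clinic visits.

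**AE questions.** Section 9.5 has AEs assessed at every scheduled follow-up visit. In Appendices L, N and O the row "Intercurrent illness/adverse experience" has its last mark at that same final visit and is blank at Post. The only Post mark is confirmation that the participant received the HIV result. The footnotes to the HIV assessment row add: "A subsequent follow-up contact is conducted to provide post-test counseling and to report results to participant".

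**After a biopsy.** Section 4.8 expects healing within 5 to 14 days. Section 9.6 tells participants to contact the clinic for heavy bleeding, a temperature above 38.1°C, chills, or pain that does not improve.

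**Reporting.** Under Section 11.2.3 the SAE category applies "from the first study product administration until the last scheduled clinic visit"; afterwards "only Suspected, Unexpected Serious Adverse Reactions as defined in Version 2.0 of the DAIDS EAE Manual must be reported to DAIDS". Section 11.2.2 states no end date for other routes: "All AEs are reported to the SDMC on the appropriate CRF"; "Sites are expected to notify the CSS or RML of any serious safety concern requiring their attention"; and "site investigators are required to submit AE information in accordance with IRB/EC and any applicable RE requirements".

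**Analysis.** SAP 8.4.2 and 9.1 tabulate AEs by relationship to mucosal sampling. The SAE listing (8.4.2) and the expedited-event table (9.1) are confined to events reported to the DAIDS Regulatory Support Center.

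**The concern.** Biopsy complications appear after the procedure, so the AE question at the visit when a biopsy is taken mostly asks about the interval before it. Earlier biopsies are covered by the question at a later visit. The final biopsy has no such visit, although it is the fifth or seventh in the series and so the one with the greatest cumulative sampling.

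Mild events are the ones most likely to be lost. A cited trial of repeated rectal biopsies in 65 volunteers (Section 4.8) reported grade 1 rectal bleeding in 1, painful defecation in 2 and anal itching in 3. Itching meets none of the Section 9.6 triggers for calling the clinic, and slight bleeding or improving pain would not either.

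At stake are the AE tables by relationship to mucosal sampling and exploratory objective 6, which concerns the tolerability of repeat sampling. The acceptability questionnaire serves the same objective, but its last administration is also at the final visit, before healing.

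**Working it through.** **1. Next scheduled AE question after each biopsy visit.** The inputs are the biopsy and AE rows and visit windows of Appendices L, N and O. Where both visits include biopsies, the shortest gap is set by the rule "Mucosal biopsy collections must be at least 28 days from the previous biopsy collection".

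| Groups | Biopsy visit → next AE question | Gap in days |
|---|---|---|
| 1, 2 | V2 → V3 | 14 (nominal) |
| 1, 2 | V14 → V15 | 28–42 |
| 1, 2 | V15 → V16 | 42–70 |
| 1, 2 | V16 → V17 | 84–112 |
| 1, 2 | V17 → none | – |
| 4, 5 | V4 → V5 | 28–42 |
| 4, 5 | V5 → V7 | 14–42 |
| 4, 5 | V9 → V12 | 28–56 |
| 4, 5 | V12 → V14 | 28–56 |
| 4 | V14 → none | – |
| 5 | V14 → V16 | 70–98 |
| 5 | V16 → V17 | 84–112 |
| 5 | V17 → none | – |

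For example, V16 (days 253–267) to V17 (days 351–365) spans 351 − 267 = 84 to 365 − 253 = 112 days.

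The reading of the schedule reproduces the biopsy totals in Tables 9-1 and 9-2:
- Groups 1–2: rectal 5 × 5 = 25; cervical 4 + 4 + 2 + 2 + 2 = 14; vaginal 5 + 5 + 5 + 5 + 2 = 22.
- Group 4: 2 × 5 = 10 per compartment.
- Group 5: 2 × 7 = 14 per compartment.

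**2. Number of biopsy visits affected.** Group sizes from the SAP schema are 23, 23, 16 and 10, with full attendance assumed.
- Planned biopsy visits: 46 × 5 + 16 × 5 + 10 × 7 = 230 + 80 + 70 = 380.
- Final visits: 46 + 16 + 10 = 72, and 72/380 = 18.9%.
- By group: 46/230 = 20%, 16/80 = 20%, 10/70 = 14.3%.
- Visits with a later AE question: 380 − 72 = 308.
- With the protocol's approximate Group 5 size of 6: 68/352 = 19.3%.

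**3. Allowing for missed final biopsies.** Biopsies can be declined or stopped (Sections 7.3.5 and 9.6), so 72 is a ceiling.
- If 15% are missed (an assumption, borrowed from the missing-data allowance in Section 6.1): 72 × 0.85 = 61.2, and 61.2/(308 + 61.2) = 16.6%.
- If 30% are missed (an assumption): 72 × 0.70 = 50.4, and 50.4/(308 + 50.4) = 14.1%.

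**4. What the table does not show.** Most earlier biopsies have no AE question inside the 5-to-14-day healing period either. Only V2 in Groups 1–2 (nominally) and V5 in Groups 4–5 (at the edge of the window) can reach day 14. What the final biopsy lacks is a later opportunity for recall.

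**The case against.** The strongest reply is that a route for capture already exists. Staff contact the participant after the last visit to give the HIV result, and anything mentioned then is an AE with no stated cut-off in Section 11.2.2. This stands: what is missing is a scheduled prompt, and a reader who inferred that such events reach the tables only through a participant's call would be going too far.

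The contrast with earlier biopsies is also thin. Their next AE question mostly comes 28 to 112 days later, and early detection after every biopsy rests on the same advice to call. That too stands and limits the point to later recall.

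A question at Post also creates a different asymmetry. If the HIV-result contact falls sooner than those intervals, the final biopsy could look worse simply because it was asked about earlier. This is a real downside of the fix.

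The yield is likely to be low. Section 4.8 reports no complications in more than 150 biopsy visits at one site and more than 160 cervicovaginal biopsy visits elsewhere. The one significant event it describes did not need hospital admission. SAP 8.4.2 counts each participant once per category. A share near 20% follows simply from having five biopsy visits and says nothing about risk.

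Finally, the Study Specific Procedures were not provided and the consent forms were removed before review. Either might already describe a post-biopsy contact.

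**Conclusion.** The point holds as a small gap in scheduled ascertainment. In Groups 1, 2, 4 and 5, up to 72 of 380 planned biopsy visits (18.9%) have no later scheduled AE question, and every earlier one does. The figure assumes SAP group sizes, full attendance and that no unseen document adds a contact. Only sampling-related safety and exploratory objective 6 are affected; power and the primary pharmacokinetic analysis are untouched. It is worth considering because the remedy is nearly free.

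Three stronger readings are not supported:
- **That AE recording stops at the last visit.** Section 11.2.3 narrows only expedited reporting to DAIDS. A later serious sampling-related event not suspected to be product-related could be absent from the SAP listing of events reported to the Regulatory Support Center, but the other routes in Section 11.2.2 remain, and the mucosal-sampling AE tables state no cut-off.
- **That the tables are biased by a known amount.** The studies cited in Section 4.8 sampled differently, so no event count or bias follows from them.
- **That Group 3 has the same gap.** Its table (Appendix M) shows an AE mark under Post but may be displaced in the extracted text, so nothing is claimed.

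**What to change.** In Appendices L, N and O, mark the AE row at Post and have the question asked at the existing HIV-result contact. In SAP 8.4.2 and 9.1, state that these events enter the tables by relationship to mucosal sampling. Final biopsy visits without a later scheduled AE question then fall from 72 to 0.

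The cost is one question per participant, with no new visit or blood draw. The SAP should note that the recall interval differs from that of earlier biopsies (28 to 112 days for most) and that AE rates should not be compared across biopsy visits without saying so.

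Two additions are optional. The documents do not give the timing of the HIV-result contact; if it comes before about day 14, a short call then would cover the rest of healing, at the price of an added contact, and HIV results should not wait for it. If the Section 11.2.3 window is changed for sampling-related SAEs, it should also open at the first biopsy, because the 46 planned baseline biopsy visits in Groups 1 and 2 (day −14) precede the first infusion.
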